5.3. Power and Sample Size Calculations

A sample size of 80 evaluable participants per treatment group will provide 90% power to detect a difference of 3.1 points for the change from Baseline to Week 12 on the TETRAS composite outcome between JZP385 and placebo, with a common SD of 6.0 points. This sample size will also provide 91.7% power to detect a 26% between-treatment (assuming JZP385 at 66% versus placebo at 40%) difference in proportion of participants who improved by at least 1 point on the CGI-S from Baseline to Week 12. Assuming a 20% dropout rate, a total of 400 participants (100 participants per treatment group) will be randomized. The sample size calculation for the TETRAS composite outcome score is based on t-test and the CGI-S sample size calculation is based on chi-square test, both tests are 2-sided at the significance level of 0.05.

For the TETRAS composite outcome, at least 80% power is still achieved if there is a reduction of 0.4 points from the assumption in the difference in mean change from baseline (assuming a constant common standard deviation) or an increase in common standard deviation by 1 point, (assuming a constant difference in means). For the key secondary endpoint, at least 80% power is still achieved with comparable shifts in the assumptions.

The assumptions for these sample sizes were supported by the results from the Phase 2 study in Essential Tremor (Study CX-8998-CLN2-001 [T-CALM]), where the TETRAS ADL and PS were assessed. Using the same derived TETRAS composite outcome score, as defined in this SAP, and assessing the change from baseline to Day 28 in T-CALM, there was a difference in means between JZP385 and placebo of 3.04 and a difference in LS Means of 3.27. The standard deviation for the change from baseline was 5.86 in JZP385 and 5.47 in placebo. It is hypothesized that the treatment improvement will remain consistent over the longer study duration of JZP385-201, with a small increase in variability, thus supporting the above assumptions.

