7.4. Level of Significance & Multiplicity Adjustment

To evaluate the efficacy of JZP385 at doses of 10, 20, and 30 mg/day compared with placebo, pairwise treatment difference between each of the 3 doses and placebo will be tested at the end of Week 12 for the primary and key secondary endpoints.

The family-wise Type I error rate will be controlled at a 2-sided significance level of 0.05. To address the multiplicity issue due to the multiple efficacy endpoints and doses, a fixed hierarchical testing sequence will be employed. The testing procedure will stop when a p-value exceeds 2-sided significance level of 0.05 (see below).

Statistical hypotheses to be tested (in sequential order):

- 1. Change in the TETRAS composite outcome score from Baseline to Week 12, 30 mg/day versus placebo.
- 2. Difference in proportion of participants who improved (≥ 1 point decrease) on the CGI-S from Baseline to Week 12, 30 mg/day versus placebo.
- 3. Change in the TETRAS composite outcome score from Baseline to Week 12, 20 mg/day versus placebo.
- 4. Difference in proportion of participants who improved (≥ 1 point decrease) on the CGI-S from Baseline to Week 12, 20 mg/day versus placebo.
- 5. Change in the TETRAS composite outcome score from Baseline to Week 12, 10 mg/day versus placebo.
- 6. Difference in proportion of participants who improved (≥ 1 point decrease) on the CGI-S from Baseline to Week 12, 10 mg/day versus placebo.

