9.2. Secondary Efficacy Estimand, Endpoints and Analyses

9.2.1. Key Secondary Efficacy Estimand

The attributes of the key secondary estimand are listed in Section 4.1.2.

The CGI-S is a 5-point Likert-type ordinal scale. The responses to this investigator-completed scale range from 1 to 5 and correspond to the following categories:

- No limitations (1)
- Mild (2)

- Moderate (3)
- Marked (4)
- Severe (5)

For analysis purposes, CGI-S will be treated as a dichotomous variable where a response is defined as $a \ge 1$ -point decrease (improvement) from Baseline to Weeks 4, 8 and 12. For the estimator, the proportion of participants who have achieved the response at Week 12 will be compared between JZP385 and placebo groups.

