9.2.2. Primary Analysis

The main estimator of the key secondary estimands will be analyzed using the CMH test adjusting for the stratification factor at randomization (Baseline TETRAS composite score: ≤ 17 or > 17 and antitremor medication use at Baseline: Yes or No). Number of responders in each group, proportion as well as 95% CI (Wilson score method) will be reported at Week 12. The 2-sided p-values from the CMH test, the unadjusted treatment difference as well as the adjusted treatment difference in proportion using the weighted average of the treatment differences across strata with CMH weights, and the associated 2-sided 95% CI using a normal approximation to the weighted average will be derived and reported at Week 12.

Treatment dropouts and missing observations for the main analytic approach will be handled through multiple imputation (MI), a method that relies on observed values from similar participants who remained in the study to bridge information to deduce missing observations. Missing values at Weeks 4, 8 and 12 for CGI-S will be imputed using the MI method. The MI procedure in SAS will be used to impute a missing CGI-S score at the scheduled visit to create 20 complete datasets.

The missing data pattern will be checked at Baseline, Weeks 4, 8 and 12. If any non-monotone missing pattern is observed, 2 separate steps will be followed to complete the imputation, starting with Step 1. If a monotone missing pattern is observed, skip to Step 2 (setting imputation number to 20)

Step 1: the Markov Chain Monte Carlo (MCMC) method will be used with a single chain to impute missing CGI-S scores by treatment, baseline stratification group as well as baseline CGI-S score to create 20 imputed datasets with monotone missing patterns. Set the seed as 8715942. Imputed scores should be rounded to nearest integer, set minimum and maximum possible score to 1 and 5 respectively, which corresponds to the range of CGI-S.

Step 2: the predictive mean matching (PMM) method will be used to impute the remaining missing CGI-S scores for the 20 imputed datasets with monotone missing patterns. The imputation procedure will use monotone statement to create 1 compete dataset for each of the monotone datasets from Step 1, with model variables include treatment, baseline stratification group, as well as CGI-S score at scheduled visits from Baseline to Weeks 4, 8 and 12. Set the seed as 4985135 and number of closest observations to 2.

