The imputed datasets will be analyzed using CMH test, and the final inference will be pooled using SAS procedure MIANALYZE.

The following is an example SAS code for CMH analysis:

PROC SORT DATA = CGIS;

```
Jazz Pharmaceuticals
Statistical Analysis Plan - Protocol JZP385-201
BY IMPUTESEO VISIT TRT STRATUM DECENDING RESPONSE:
RUN;
PROC SQL;
CREATE TABLE ADDIN AS
SELECT DISTINCT IMPUTESEQ, VISIT, TRT, STRATUM, 1 AS RESPONSE
FROM CGIS;
QUIT;
DATA CMH;
MERGE CGIS (IN=A) ADDIN (IN=B);
BY IMPUTESEQ VISIT TRT STRATUM DECENDING RESPONSE;
IF B AND NOT A THEN WGT = 0;
ELSE WGT = 1;
RUN:
*Adjusted (Stratified) Difference and CMH TEST;
PROC FREQ DATA=CMH;
BY IMPUTESEO AVISITN:
TABLES STRATUM*TRT*RESPONSE/RISKDIFF (COMMON CL=(NEWCOMBE)) CMH;
WEIGHT WGT/ZEROS;
RUN;
*Unadjusted (Unstratified) Difference;
```

PROC FREQ DATA=CMH;
BY IMPUTESEQ AVISITN;
TABLES TRT*RESPONSE/RISKDIFF CMH;

WEIGHT WGT/ZEROS;

RUN;

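### The CGI-S imputation copies each missing score from only 2 donors; under one matching rule, which the SAP leaves open, the gating test is noisier and can exceed 5%

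*SAP*

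**What the plan says.** SAP 9.2.2 handles missing CGI-S scores by multiple imputation: "The MI procedure in SAS will be used to impute a missing CGI-S score at the scheduled visit to create 20 complete datasets". Step 1 fills intermittent gaps by MCMC. Step 2 fills the remaining monotone gaps by predictive mean matching, "with model variables include treatment, baseline stratification group, as well as CGI-S score at scheduled visits from Baseline to Weeks 4, 8 and 12". The donor rule is one sentence: "Set the seed as 4985135 and number of closest observations to 2". Each completed data set is analysed with the CMH test, and "the final inference will be pooled using SAS procedure MIANALYZE".

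SAP 9.2.1 states that "The CGI-S is a 5-point Likert-type ordinal scale"; a drop of at least 1 point counts as response. In SAP 7.4 the CGI-S comparisons are hypotheses 2, 4 and 6 of a fixed sequence, so hypothesis 2 (30 mg/day) gates everything below it. The same section promises that "The family-wise Type I error rate will be controlled at a 2-sided significance level of 0.05".

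The same donor number appears in Step 2 of SAP 9.1.3.1, and SAP 9.2.6.1 and 9.3.2 reuse the CGI-S imputation. Protocol 9.4.3.1 names predictive mean matching but gives no donor number.

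**The concern.** Rubin's rules add the within-imputation variance W to the between-imputation variance B: T = W + (1 + 1/20)B for 20 data sets. B is meant to carry the uncertainty about the missing scores. With a pool of 2, the same two people can be drawn again and again across the 20 data sets, which holds B down. Single donors also carry more weight, which makes the estimate itself noisier. More imputations do not help, because the pool stays at two. The predictors are all discrete, so predicted means often tie, and the tie rule then decides who donates.

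At stake is a gating test. If 30 mg works on TETRAS but not on CGI-S, a standard error that is too small raises the chance of a false CGI-S claim and of opening the gate to the lower doses.

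**Working it through.** **1. The plan's own figures (SAP 5.3).** CGI-S power, 66% versus 40%, 80 per arm, pooled chi-square:
- null SE = √(2 × 0.53 × 0.47 / 80) = 0.0789
- alternative SE = √((0.66 × 0.34 + 0.40 × 0.60) / 80) = 0.0762
- z = (0.26 − 1.96 × 0.0789) / 0.0762 = 1.38, so power is 91.7%, as stated.

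Randomised per arm = 80 / 0.80 = 100, as stated. The sizing is not in question.

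**2. Simulation inputs.** From the documents: four arms of 100, 20 imputations, the Step 2 predictors, 40% response (the planning value for placebo) and about 20% dropout. Assumed: the correlation between visits, a missing-at-random dropout mechanism, and a stress case with about 42% missing on 30 mg and 21% on placebo. The null is true. The test is the CMH-weighted risk difference, 30 mg versus placebo, pooled by Rubin's rules. There were 2,500 trials per case, so the Monte Carlo SE is √(0.05 × 0.95 / 2500) = 0.44 points.

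**3. Two matching rules.** *Same draw*: donor and recipient predictions use the same random draw of the regression coefficients. *Fitted*: donor predictions use the fitted coefficients and recipient predictions use a draw.

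**4. Results.** Ratio = mean pooled SE / SD of the estimate.

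| Donors, matching, ties | SD (21% missing) | Ratio | Type I error | SD (42% on 30 mg) | Ratio | Type I error |
|---|---|---|---|---|---|---|
| Full data | 0.0690 | 0.990 | 5.2% | 0.0690 | 0.990 | 5.2% |
| Completers | 0.0771 | 0.999 | 5.0% | 0.0843 | 0.990 | 5.5% |
| 2, same draw, random | 0.0760 | 0.967 | 5.8% | 0.0824 | 0.925 | 8.1% |
| 2, same draw, data order | 0.0784 | 0.923 | 7.6% | 0.0872 | 0.861 | 9.2% |
| 5, same draw, random | 0.0745 | 0.998 | 5.0% | 0.0793 | 0.983 | 6.2% |
| 10, same draw, random | 0.0728 | 1.028 | 4.5% | 0.0771 | 1.026 | 4.6% |
| 10, same draw, data order | 0.0730 | 1.027 | 4.4% | 0.0769 | 1.028 | 4.9% |
| 2, fitted, random | 0.0730 | 1.054 | 4.1% | 0.0777 | 1.074 | 3.7% |
| 10, fitted, random | 0.0721 | 1.050 | 3.9% | 0.0760 | 1.063 | 4.3% |

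**5. Plausibility.** With SE ratio r, a normal test rejects about 2Φ(−1.96r). For r = 0.967 this is 5.8%, for 0.861 it is 9.2%, and for 1.054 it is 3.9%, close to the simulated 5.8%, 9.2% and 4.1%.

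**6. Size of the noise at planned dropout, same draw.** 0.0760 / 0.0728 = 1.04 and 0.0784 / 0.0730 = 1.07 against 10 donors; 0.0760 / 0.0745 = 1.02 against 5. Under fitted matching, 0.0730 / 0.0721 = 1.01.

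**7. Other simulations of the same design, same draw.**
- 19.5% missing, 3,500 to 4,000 trials: 2 donors gave SD 0.0751 to 0.0763 and 5.6 to 6.1%; 5 donors gave 0.0732 and 5.0%.
- 21% missing, 1,800 trials: 2 donors gave SD 0.0761 to 0.0769 and 5.7 to 5.9%; 5 donors gave 0.0737 to 0.0739 and 4.8 to 4.9%. Under fitted matching, 2 donors gave 3.8%.
- 21% missing, about 56% responders, 3,768 trials: 2 donors gave 5.8% (random ties) and 6.4% (data order); 5 donors gave 4.6%.

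**The case against.** **The documents do not say which matching rule applies.** A reader might infer that the pooled standard error is too small. The SAP does not support that: it names the SAS procedure but no matching or tie rule, and under fitted matching the standard error is slightly too large. This stands, and it makes the error-control point conditional.

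**The simulated test is not the planned p-value.** The SAP takes its p-value from the CMH test. In a run of 2,500 null trials with about 20.5% missing and same-draw matching, complete data gave 6.0% (risk difference) and 5.4% (CMH). Two donors gave 5.8% and 5.3% with random ties, and 6.6% and 6.2% with data-order ties; the CMH figures pool the CMH score, which is one reading of the SAP. With random ties neither test exceeded its own complete-data rate. This stands: at planned dropout, the random-tie excess is close to simulation noise.

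**Missingness may be lower.** Early-discontinuation visits collect CGI-S (Protocol 1.3), SAP 7.2.3 maps Days 71 to 98 to Week 12, and Step 1, not the donors, fills intermittent gaps. At 14.8% missing with random ties the rates were 5.6% and 4.9%. The 42% case has no source in the documents and is a stress test only.

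**Other analyses do not use donors.** Non-responder imputation, the tipping-point grid and the completers analysis (SAP 9.2.3 and 9.2.4) could expose a result that hangs on imputed scores. They do not vary the donor number or repair the gating p-value.

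**A reader might also infer that 2 donors waste most of the gain over completers.** That does not hold in general. Measured against 5 donors with same-draw matching and random ties, about half is lost: (0.0765 − 0.0741) / (0.0787 − 0.0741) = 52% in the 20.5% run and (0.0760 − 0.0745) / (0.0771 − 0.0745) = 58% in the main run. Against 10 donors the main-run share is larger (0.0032 / 0.0043 = 74%). Under fitted matching little or nothing is lost. With data-order ties and same-draw matching the gain disappears.

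**Conclusion.** The point holds in conditional form. With same-draw matching, 2 donors make the CGI-S estimate noisier than it need be and can make its pooled standard error too small. The size then depends on the tie rule and on dropout: an excess of under 1 point with random ties at planned dropout, up to 7.6% with data-order ties, and 8.1 to 9.2% in the stress case. With fitted matching the test is conservative. The documents do not settle which case applies, so this is an avoidable risk to the promised 0.05 control, not a demonstrated breach of it.

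The figures rest on assumed dropout and correlation models and on a pooled risk-difference test. No effect was shown for the pattern-mixture analysis in SAP 9.1.3.1, which imputes a 0 to 42 score and is a sensitivity analysis only. The change is still worth making: a larger pool did no harm under either matching rule and improved both precision and error control under same-draw matching.

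**What to change.** In SAP 9.2.2 Step 2, before unblinding, replace 2 closest observations with a fixed larger number, about 10, and state that ties are broken at random. Five is adequate at planned dropout but still gave 6.2% in the heavy 30 mg dropout case. Record the matching rule that the software applies, so that a reader can tell which case holds. Use the same donor number in SAP 9.1.3.1 for consistency.

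The cost is one number in two SAP paragraphs and a line on ties and matching. No data, estimand, test or test order changes, and no protocol amendment is needed for the number because Protocol 9.4.3.1 does not fix it. With 10 donors the tie rule hardly mattered (4.5% against 4.4% at planned dropout), so little is lost if the software gives limited control over ties.

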9.2.3. Sensitivity Analyses

Sensitivity analyses will be conducted to account for missing data using NRI (Non-responder Imputation) method and 2-dimensional tipping point analyses.

For NRI, participants who have insufficient data (due to missingness) for response determination will be considered as non-responder (< 1 point change from Baseline) for Week 12. Then a similar stratified/unstratified CMH test will be conducted, and results will be reported.

For the 2-dimensional tipping point analyses, let M1 and M2 be the total number of participants with missing CGI-S data in the JZP385 and Placebo groups, respectively. There will be a total of (M1+1)*(M2+1) possible ways end up with imputing missing values to a result of responder or non-responder in each of the 2 groups. For each of the (M1+1)*(M2+1) imputation patterns, a Chi-square test will be conducted to test the statistical significance, and the output will be displayed in a rectangle shape. The staircase region that separates significant and non-significant outcomes forms the tipping-point boundary.

9.2.4. Completers Analysis (Data as Observed)

The primary analysis in Section 9.2.2 will be conducted to only include the participants who have the CGI-S at Week 12. This constitutes a Completers Analysis. The corresponding CMH analysis will be used from the primary analysis.

9.2.5. Subgroup Analyses

Subgroup analyses for groups specified in Section 7.5 will be performed for the key secondary efficacy estimand using ITT. The analysis in Section 9.2.2 will be used for the subgroup analyses. However, the randomization stratification factor will be removed from the model for the analysis by subgroups of participants by randomization strata.

9.2.6. Other Secondary Endpoints and Analyses

9.2.6.1. CGI-C and PGI-C at Week 12

The secondary efficacy endpoint of CGI-C is defined as the proportion of investigators reporting improvement of symptoms ("much improved") on CGI-C at Week 12. The CGI-C is a 5-point Likert-type rating scale. Investigators will rate their impression of any change in severity of the subject's condition on a 5-point scale ranging from 1 = "much improved" to 5 = "much worse" since Baseline. Clinicians' rating will focus on the change in the patients' ability to function due to ET.

The proportion of participants reporting improvement of symptoms on CGI-C will be compared between treatment groups using the Cochran-Mantel-Haenszel (CMH) test stratified by randomization stratum. The point estimate and continuity corrected Wilson's 95% CI (as modified by Newcombe) for the difference of the proportion will also be provided.

Similarly, the secondary efficacy endpoint of PGI-C is defined as the proportion of participants reporting improvement of symptoms ("much improved") on PGI-C at Week 12. The PGI-C is a 5-point Likert-type rating scale. Participants will rate the change in their condition since Baseline on a 5-point scale ranging from 1 = "much improved" to 5 = "much worse". Participants' rating will focus on the change in their ability to function due to ET.

The proportion of participants reporting improvement of symptoms on PGI-C will be compared between treatment groups using the Cochran-Mantel-Haenszel (CMH) test stratified by randomization stratum. The point estimate and continuity corrected Wilson's 95% CI (as modified by Newcombe) for the difference of the proportion will also be provided.

Treatment dropouts and missing observations will be handled by multiple imputation (MI) as stated in Section 9.2.2. No sensitivity analyses or supplemental analysis planned.

9.2.6.2. Change from Baseline to Week 12 on the TETRAS-ADL, TETRAS-PS, TETRAS-PS upper limb score (item 4), and TETRAS total score

The secondary efficacy endpoints of change from Baseline to Week 12 on:

- TETRAS-ADL (sum of 12 items, each rated 0, 1, 2, 3 or 4. The maximum total score is 48)
- TETRAS-PS (sum of 9 items rated from 0-4 with half points and a maximum total score of 64)

- TETRAS-PS upper limb score (item 4)
- TETRAS total score (sum of the TETRAS-ADL and TETRAS-PS)

will be analyzed similarly with MMRM. The MMRM will include the difference from Baseline to Weeks 4, 8, and 12. The model will include treatment group, corresponding baseline, week (as a discrete factor), treatment group by week interaction, and randomization stratum as fixed effects, and participant as a random effect. If the model fails to converge on the Newton-Raphson Algorithm, the alternative Fisher scoring algorithm should be explored before considering other variance-covariance structures. The first alternative variance-covariance matrix will be autoregressive. Kenward-Roger's degrees of freedom will be used.

LS mean and SE for Week 12 will be provided for each treatment group. The difference between the LS means of JZP385 and placebo for Week 12, along with the SE of the difference, 95% CI and associated p-value corresponding to the testing hypothesis of no difference between the treatment groups will also be provided.

The assumption of normality will be examined by obtaining a histogram and a QQ-plot on studentized residuals. Based on these plots, if there is evidence to suggest the departure from the normality assumption, a non-parametric MMRM with the covariate and response variables replaced by their ranks will be used.

